### **17.4.1.9. Liver Disorders**

#### **17.4.1.9.1. ICD-10-CM Codes**

- K70.10 Alcoholic hepatitis without ascites
- K70.11 Alcoholic hepatitis with ascites
- K70.2 Alcoholic fibrosis and sclerosis of liver
- K70.30 Alcoholic cirrhosis of liver without ascites
- K70.31 Alcoholic cirrhosis of liver with ascites
- K70.40 Alcoholic hepatic failure without coma
- K70.41 Alcoholic hepatic failure with coma
- K70.9 Alcoholic liver disease, unspecified
- K71.0 Toxic liver disease with cholestasis
- K71.10 Toxic liver disease with hepatic necrosis, without coma
- K71.11 Toxic liver disease with hepatic necrosis, with coma
- K71.2 Toxic liver disease with acute hepatitis
- K71.3 Toxic liver disease with chronic persistent hepatitis
- K71.4 Toxic liver disease with chronic lobular hepatitis
- K71.50 Toxic liver disease with chronic active hepatitis without ascites
- K71.51 Toxic liver disease with chronic active hepatitis with ascites
- K71.6 Toxic liver disease with hepatitis, not elsewhere classified
- K71.7 Toxic liver disease with fibrosis and cirrhosis of liver
- K71.8 Toxic liver disease with other disorders of liver
- K71.9 Toxic liver disease, unspecified K72 Hepatic failure, not elsewhere classified Includes: fulminant hepatitis NEC, with hepatic failure
- K72.00 Acute and subacute hepatic failure without coma
- K72.01 Acute and subacute hepatic failure with coma

- K72.10 Chronic hepatic failure without coma
- K72.11 Chronic hepatic failure with coma
- K72.90 Hepatic failure, unspecified without coma
- K72.91 Hepatic failure, unspecified with coma
- K73.0 Chronic persistent hepatitis, not elsewhere classified
- K73.1 Chronic lobular hepatitis, not elsewhere classified
- K73.2 Chronic active hepatitis, not elsewhere classified
- K73.8 Other chronic hepatitis, not elsewhere classified
- K73.9 Chronic hepatitis, unspecified
- K74.0 Hepatic fibrosis
- K74.1 Hepatic sclerosis
- K74.2 Hepatic fibrosis with hepatic sclerosis
- K74.3 Primary biliary cirrhosis
- K74.4 Secondary biliary cirrhosis
- K74.5 Biliary cirrhosis, unspecified
- K74.60 Unspecified cirrhosis of liver
- K74.69 Other cirrhosis of liver
- K75.0 Abscess of liver
- K75.1 Phlebitis of portal vein
- K75.2 Nonspecific reactive hepatitis
- K75.3 Granulomatous hepatitis, not elsewhere classified
- K75.4 Autoimmune hepatitis
- K75.81 Nonalcoholic steatohepatitis (NASH)
- K75.89 Other specified inflammatory liver diseases

K75.9	Inflammatory liver disease, unspecified
K76.0	Fatty (change of) liver, not elsewhere classified
K76.1	Chronic passive congestion of liver
K76.2	Central hemorrhagic necrosis of liver
K76.3	Infarction of liver
K76.4	Peliosis hepatis
K76.5	Hepatic veno-occlusive disease
K76.6	Portal hypertension
K76.7	Hepatorenal syndrome
K76.81	Hepatopulmonary syndrome
K76.89	Other specified diseases of liver
K76.9	Liver disease, unspecified
K77	Liver disorders in diseases classified elsewhere

#### **17.4.1.10. Neurological or Neurodevelopmental Conditions**

##### **17.4.1.10.1. ICD-10-CM Codes**

F70	Mild intellectual disabilities
F71	Moderate intellectual disabilities
F72	Severe intellectual disabilities
F73	Profound intellectual disabilities
F78	Other intellectual disabilities
F79	Unspecified intellectual disabilities
F80.0	Phonological disorder
F80.1	Expressive language disorder
F80.2	Mixed receptive-expressive language disorder
F80.4	Speech and language development delay due to hearing loss

- F80.81 Childhood onset fluency disorder
- F80.82 Social pragmatic communication disorder
- F80.89 Other developmental disorders of speech and language
- F80.9 Developmental disorder of speech and language, unspecified
- F81.0 Specific reading disorder
- F81.2 Mathematics disorder
- F81.81 Disorder of written expression
- F81.89 Other developmental disorders of scholastic skills
- F81.9 Developmental disorder of scholastic skills, unspecified
- F82 Specific developmental disorder of motor function
- F84.0 Autistic disorder
- F84.2 Rett's syndrome
- F84.3 Other childhood disintegrative disorder
- F84.5 Asperger's syndrome
- F84.8 Other pervasive developmental disorders
- F84.9 Pervasive developmental disorder, unspecified
- F89 Unspecified disorder of psychological development

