### 9.3.3. Covariates

All members of the study cohorts will be described according to covariates identified in the claims data. Demographic attributes will be determined on the vaccination/cohort entry date, while other factors will be assessed in the one year prior to the cohort entry date. Unless specified as for descriptive purposes only, the covariates listed will be included in the PS models. All variables are binary unless otherwise specified.

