#### Comorbidities

- Asthma
- Non-malignant blood disorders, including sickle cell disease
- Chronic lung disease, including chronic obstructive pulmonary disease (COPD)
- Down syndrome
- Heart disease
- History of SARS-CoV-2 infection
- Immunocompromised status (i.e., history of human deficiency virus [HIV]; organ, bone marrow or stem cell transplant; use of immunosuppressant medication)
- Kidney disorders, including chronic kidney disease
- Liver disorders
- Neurological or neurodevelopmental conditions
- Malignant neoplasms
- Obesity
- Type 2 diabetes

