### **COVID-19 Vaccination – Descriptive only (not for inclusion in PS model)**

- Site of vaccination (e.g., outpatient, pharmacy)
- Source of vaccination information (e.g., CPT code, NDC)
- Number of doses prior to 2023-2024, by vaccine product
- Average number of days between doses of COMIRNATY 2023-2024 Formula, among those with multiple doses

Code lists for covariates are included in [Appendix IV](#).

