$$\begin{aligned} & \text{logit}\{P(T_i = 1 \mid \mathbf{X}_i)\} \\ &= \beta_0 + \beta_1 \text{Sex (binary)}_i + \beta_2 \text{Age (categorical)}_i \\ &+ \beta_3 \text{Calendar month (categorical)}_i + \beta_4 \text{Geographic region (categorical)}_i \\ &+ \beta_5 \text{Asthma (binary)}_i + \beta_6 \text{Non-malignant blood disorders (binary)}_i \\ &+ \beta_7 \text{Chronic lung disease (binary)}_i + \beta_8 \text{Down syndrome (binary)}_i \\ &+ \beta_9 \text{Heart disease (binary)}_i \\ &+ \beta_{10} \text{History of SARS-CoV-2 infection (binary)}_i \\ &+ \beta_{11} \text{Immunocompromised status (binary)}_i \\ &+ \beta_{12} \text{Kidney disorders (binary)}_i + \beta_{13} \text{Liver disorders (binary)}_i \\ &+ \beta_{14} \text{Neurological or neurodevelopmental conditions (binary)}_i \\ &+ \beta_{15} \text{Malignant neoplasms (binary)}_i + \beta_{16} \text{Obesity (binary)}_i \\ &+ \beta_{17} \text{Type II diabetes (binary)}_i \\ &+ \beta_{18} \text{Number of hospitalizations in prior year (continuous)}_i \\ &+ \beta_{19} \text{Number of emergency room visits in prior year (continuous)}_i \\ &+ \beta_{20} \text{Number of outpatient encounters in prior year (continuous)}_i \\ &+ \beta_{21} \text{Seasonal influenza vaccination (binary)}_i \\ &+ \beta_{22} \text{RSV vaccination (binary)}_i + \beta_{23} \text{Systemic immunomodulators (binary)}_i \\ &+ \beta_{24} \text{Oral corticosteroids (binary)}_i + \beta_{25} \text{Antivirals (binary)}_i \\ &+ \beta_{26} \text{Antibiotics (binary)}_i + \beta_{27} \text{Identified empiric variables (binary)}_i, \end{aligned}$$

where  $T_i$  denotes exposure status for individual  $i$ , with  $T_i = 1$  indicating a recorded vaccination of the COMIRNATY 2023-2024 Formula and  $T_i = 0$  indicating no recorded vaccination of the COMIRNATY 2023-2024 Formula.

A greedy digit-based matching algorithm will be used, in which patients exposed to the COMIRNATY 2023-2024 Formula are matched without replacement to comparator patients at a given level of precision defined by the number of digits of the PS (Parsons, 2001), to a maximum of 8 decimal places. When no further matches are available at a given level of precision, the number of digits is sequentially reduced until a maximum allowable caliper of 0.1 is reached, thereby ensuring that the matched cohorts are comparable with respect to the underlying measured risk factors. Matching by propensity score will be conducted within

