#### 9.7.2.4. Subgroup Analysis

If sample size permits, the main analysis will be restricted to the following subgroups:

- Individuals with concomitant administration of a non-COVID-19 vaccine (e.g., seasonal influenza, RSV) on cohort entry date; specific analyses will be performed among individuals receiving seasonal influenza vaccine and those receiving RSV vaccine
- Immunocompromised individuals
- Individuals with specific baseline comorbidities, such as a chronic lung, heart, kidney or liver condition; cancer; Down syndrome or other neurological or neurodevelopmental disorders; and blood disorders
- Individuals with prior SARS-CoV-2 infection
- Individuals with prior COVID-19 vaccination
- Pregnant women
- Individuals aged < 18 years
- Individuals aged  $\geq$  65 years

For the subgroup analysis, the propensity score will be included in the model as a covariate, given that some matched strata may be broken by restricting both the COMIRNATY 2023-2024 Formula cohort and the comparator cohort by the above attributes. As with the primary analysis, unconditional Poisson regression will be used, and the model will account for individuals who are included in both groups.

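### The Phase 2 covariate and subgroup named for neurological or neurodevelopmental disease are defined only by F70–F89 developmental codes, so no pre-specified propensity score term captures neurological disease as such; seizures are the main outcome affected

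*Protocol*

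**What the plan says.** Protocol Section 9.3.3 lists "Neurological or neurodevelopmental conditions" among the comorbidities and states: "Unless specified as for descriptive purposes only, the covariates listed will be included in the PS models". The model in Section 9.7.2.1 carries it as one binary term (coefficient β14), the only term named for neurological disease. Section 9.7.2.4 plans a comorbidity subgroup that includes "Down syndrome or other neurological or neurodevelopmental disorders", if sample size permits.

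The operational definition is in the annex. Section 9.3.3 ends with "Code lists for covariates are included in" Appendix IV. There, Section 17.4.1.10 starts at F70 ("Mild intellectual disabilities"), runs through entries such as "F84.9 Pervasive developmental disorder, unspecified" and ends at "F89 Unspecified disorder of psychological development".

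The document describes itself in Section 7 as a combined protocol and SAP, and Annex 1 lists no standalone documents. Some vaccine and drug lists in Annex 2 allow codes or therapies to be added later; Section 17.4.1.10 has no such clause.

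**The concern.** The name and the code list describe different things. The name promises control for neurological disease; the list covers intellectual disability and developmental disorders. A programmer who follows the annex will build a variable that misses epilepsy, demyelinating disease, neuropathy and prior cerebrovascular disease. A reader of the report will see the variable's name and assume that these are balanced. The subgroup has the same fault.

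This matters because many of the safety outcomes are neurological, and Section 9.7.2.1 relies on a wide set of outcome predictors in the PS to keep residual confounding small. Standardized differences are checked only for covariates in the model, so the planned diagnostics would not show neurological disease at all. Section 9.9 does not list the gap among the limitations.

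**Working it through.** **1. Content of the code list (17.4.1.10).** F70–F73, F78 and F79: 6 codes. F80.x: 8. F81.x: 5. F82: 1. F84.x: 6. F89: 1. Total 6 + 8 + 5 + 1 + 6 + 1 = 27, all within F70–F89, none in G00–G99 or I60–I69. The other comorbidity lists in 17.4.1 contain no G00–G99 or I60–I69 code either.

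**2. Outcomes concerned (9.3.2, 17.3).** Of 20 outcomes, seven neurological ones are defined by G codes (seizures also by R56 codes): ADEM, Bell's palsy, seizures, encephalomyelitis, Guillain-Barré syndrome, multiple sclerosis (MS) and transverse myelitis. Three are cerebrovascular and defined by I6x codes: cerebral venous sinus thrombosis (CVST), hemorrhagic stroke and ischemic stroke. That is 10 of 20 with the cerebrovascular outcomes, 7 of 20 without.

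**3. What the clean periods already remove (Table 2).** The covariate look-back is 365 days. A clean period removes prior codes for the same outcome only.

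| Outcome | Clean period | Look-back days not covered |
|---|---|---|
| ADEM | 28 days | 365 − 28 = 337 |
| Seizures, non-febrile | 42 days | 365 − 42 = 323 |
| Bell's palsy, encephalomyelitis | 183 days | 365 − 183 = 182 |
| CVST, Guillain-Barré, MS, both strokes, transverse myelitis | 365 days | 0 |

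For the last row, same-disease history in the look-back is already excluded. What remains there is related but different disease; prior MS, for example, does not exclude anyone from the transverse myelitis analysis.

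**4. Why seizures stand out.** Appendix III accepts a single code, including the chronic epilepsy codes G40.x. Table 2 accepts inpatient or outpatient care. Cohort follow-up runs up to one year. A person with known epilepsy and no qualifying claim in the 42 days before entry is eligible, and the next outpatient visit coded G40.x counts as an event. Baseline epilepsy is neither excluded nor named in the PS.

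**5. Possible size (assumed inputs).** Let p1 and p0 be the epilepsy prevalence among eligible recipients and comparators, and r the ratio of seizure-event rates with against without epilepsy. If matching on the other terms removes none of the difference, the rate ratio is multiplied by [1 + p1(r − 1)] / [1 + p0(r − 1)].

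| p1 | p0 | r = 50 | r = 20 |
|---|---|---|---|
| 0.9% | 1.2% | 1.441 / 1.588 = 0.91 | 1.171 / 1.228 = 0.95 |
| 0.8% | 1.5% | 1.392 / 1.735 = 0.80 | 1.152 / 1.285 = 0.90 |

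Exchanging p1 and p0 gives the reciprocals, 1.05 to 1.25. The protocol supplies none of these inputs.

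**6. Would the balance rule catch it?** The standardized difference is |p1 − p0| / √{[p1(1 − p1) + p0(1 − p0)] / 2}. For 0.9% against 1.2% it is 0.003 / 0.1019 = 0.03. For 0.8% against 1.5% it is 0.007 / 0.1066 = 0.07. Both are below the 0.1 threshold in Section 9.7.2.1, so even a correctly coded epilepsy variable would be called balanced.

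**The case against.** The strongest reply is that the plan has other protections.

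- **Other PS terms.** CNS cancers fall within malignant neoplasms, neuropathy codes within type 2 diabetes, and MS drugs within systemic immunomodulators. Rett's syndrome is in the F84 codes, and utilization counts are in the model. A reader might infer from the code list that no neurological disease is adjusted for at all. The documents do not support that: what is missing is a pre-specified term for it. Still, these broad indicators do not separate out neurological disease, and none is an epilepsy indicator.
- **Clean periods.** A reader might infer that all ten neurological outcomes are equally exposed. They are not: six already exclude same-disease history over the whole look-back. This stands and narrows the point to seizures first, then ADEM, Bell's palsy and encephalomyelitis.
- **Discretionary provisions.** The screen of the 25 most frequent diagnoses, drugs and procedures could bring in a neurological code, and Section 9.7.2.1 allows a separate PS model for an outcome-specific confounder. Both are only to be considered, so neither guarantees adjustment.
- **Phase 1.** The self-controlled analysis covers the same 20 outcomes, is repeated in the final report and removes time-fixed confounding. This stands: the point concerns Phase 2 only, which has its own primary objective.
- **Balance table.** A reader might infer that correct coding would make the imbalance visible there. Step 6 shows that it need not.

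**Conclusion.** The mismatch between name and definition can be verified on the page and needs no assumption. As written, the Phase 2 PS, balance check and neurological subgroup contain no pre-specified measure of neurological disease as such. The clearest consequence is for non-febrile seizures, where established epilepsy is left eligible and unadjusted. Shorter clean periods for ADEM, Bell's palsy and encephalomyelitis, and related but different disease for the other neurological outcomes, are lesser concerns.

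The bias cannot be sized from the documents. The range of 0.80 to 0.95 on the seizure rate ratio rests on assumed prevalences, on 20-fold and 50-fold event-rate ratios, on recipients having less epilepsy, and on no attenuation from other PS terms. In that direction the result would look falsely reassuring; in the opposite direction it could look like excess risk. A reader might infer that the study is biased toward safety, but the protocol gives no basis for either direction. The point should be corrected before the Phase 2 results are relied on for seizures.

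**What to change.** - Add baseline neurological disease to Appendix IV as one or more separate binary covariates: G-chapter diagnoses plus I60–I69 cerebrovascular disease. G codes alone would leave prior cerebrovascular disease uncovered for CVST and the two stroke outcomes.
- Make epilepsy (G40.x) its own term, since one pooled neurological indicator would balance it only in part.
- Use these covariates in the PS model, the balance table and the neurological subgroup. Show epilepsy prevalence by cohort beside its standardized difference, because the 0.1 rule is insensitive at low prevalence.
- Rename the F70–F89 variable as neurodevelopmental conditions wherever it appears (9.3.3, 9.7.2.1, 9.7.2.4, 17.4.1.10).

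**Cost.** No new data are needed, but the work is more than a code-list edit. One PS model produces the master cohort for all Phase 2 analyses, so the PS must be re-estimated and Phase 2 re-matched and rerun. Version 3.0 is dated 18 March 2026 and the final report is planned for 30 April 2026, 43 days later, so timing is the real constraint.

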#### **17.4.1.11. Malignant Neoplasms**

##### **17.4.1.11.1. ICD-10-CM Codes**

- C00-C14 Malignant neoplasms of lip, oral cavity and pharynx
- C15-C26 Malignant neoplasms of digestive organs
- C30-C39 Malignant neoplasms of respiratory and intrathoracic organs
- C40-C41 Malignant neoplasms of bone and articular cartilage
- C43-C44 Melanoma and other malignant neoplasms of skin
- C45-C49 Malignant neoplasms of mesothelial and soft tissue

- C50 Malignant neoplasms of breast
- C51-C58 Malignant neoplasms of female genital organs
- C60-C63 Malignant neoplasms of male genital organs
- C64-C68 Malignant neoplasms of urinary tract
- C69-C72 Malignant neoplasms of eye, brain and other parts of central nervous system
- C73-C75 Malignant neoplasms of thyroid and other endocrine glands
- C7A Malignant neuroendocrine tumors
- C7B Secondary neuroendocrine tumors
- C76-C80 Malignant neoplasms of ill-defined, other secondary and unspecified sites
- C81-C96 Malignant neoplasms of lymphoid, hematopoietic and related tissue

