#### 9.7.2. Cohort Study

##### 9.7.2.1. Propensity Score Modeling and Matching

The COMIRNATY 2023-2024 Formula-exposed and the unexposed comparator cohorts will be created as described in [Section 9.2.3](#). Each cohort member will be described with respect to baseline covariates as listed in [Section 9.3.3](#). These cohort members will be included in the propensity score modeling and matching.

This study will use a single PS model that encompasses risk factors for multiple outcomes, an approach demonstrated in other studies conducted to fulfill post-licensure regulatory commitments and requirements to the FDA and other regulatory agencies ([Seeger et al., 2023](#); [Ziyadeh et al., 2020](#)). While not all risk factors may be associated with all outcomes to the same degree, adjusting for covariates that are weakly or not at all associated with a given outcome is expected to result in negligible bias if residual confounding is small ([Brookhart et al., 2006](#); [Myers et al., 2011](#)). Incorporating a wide array of outcome predictors

(Section 9.3.3) into the PS is expected to minimize residual confounding, producing groups with similar patterns of both measured and unmeasured factors (Guertin et al., 2016).

The PS model will consist of a logistic regression model that incorporates the pre-specified demographic and comorbidity covariates, healthcare utilization, and calendar month of vaccination or cohort entry as independent variables, and an indicator for receipt of the COMIRNATY 2023-2024 Formula as the dependent variable. Two-way interactions of all variables with calendar month of vaccination or cohort entry, or empirically defined variables that are potential confounders, may also be considered for inclusion in the following model:

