strata defined by age group and calendar period. A matching ratio (e.g., up to 1:10) may be implemented.

PS matching will produce a single matched cohort (the master cohort) that will be used to conduct all primary, secondary, and sub-group analyses for the study outcomes. Balance between the PS-matched cohorts will be evaluated by overlaying graphs of the PS distributions in COMIRNATY-exposed and comparator cohorts before and after PS matching. Additionally, standardized differences between the PS-matched cohorts for each covariate in the model will also be assessed. Variables with an absolute standardized difference less than 0.1 will be considered balanced (Austin, 2009). If a variable has a standardized difference that is greater than 0.1, further PS model modifications (e.g., addition of interaction terms) or inclusion of the imbalanced covariates in an outcome model will be considered (Normand et al., 2001). If there are confounders identified that would only be appropriate to include for one outcome and not the others, a separate PS model for the specific outcome will be considered.

Outcome-specific exclusion criteria will be applied to the master cohort after PS matching but before the outcome specific analysis; the matched cohort that remains will be the analytic cohort for that specific outcome. The matched comparators of individuals excluded for outcome-specific exclusion criteria will also be excluded from the outcome-specific analysis.

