#### **17.4.2.1.3. Chemotherapeutic Agents**

##### **17.4.2.1.3.1. Alkylating Agents**

chlorambucil  
cisplatin  
cyclophosphamide

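### One binary malignancy term pools C44 with all other cancers, so matching need not balance the other cancers, and the cancer subgroup includes C44-only patients

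*Protocol*

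**What the plan says.** The malignant-neoplasm code list (Section 17.4.1.11.1) runs from C00 to C96 and includes the line "C43-C44 Melanoma and other malignant neoplasms of skin". Section 9.3.3 states that "All variables are binary unless otherwise specified", and malignant neoplasms has no exception. The PS equation in Section 9.7.2.1 gives it one coefficient, with no split by type or activity.

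The same section states that "This study will use a single PS model that encompasses risk factors for multiple outcomes". On diagnostics it says that "standardized differences between the PS-matched cohorts for each covariate in the model will also be assessed", and that "Variables with an absolute standardized difference less than 0.1 will be considered balanced".

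Section 9.7.2.4 plans a subgroup of "Individuals with specific baseline comorbidities, such as a chronic lung, heart, kidney or liver condition; cancer". There is no other cancer code list, so I take the Section 17.4.1.11 list to define that subgroup. Nothing in the protocol separates C44 or explains the pooling. Section 7 describes the document as a combined protocol and SAP, so this is where the definition is fixed.

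**The concern.** A flag that joins two groups with different outcome risk balances the mixture, not the risk. The Section 9.3.2 outcomes include pulmonary embolism, cerebral venous sinus thrombosis, both strokes and immune thrombocytopenia. Suppose other cancers raise the rate of such an outcome and C44 alone does not. Then two matched groups with the same flag prevalence can still differ in risk if the share of C44 within the flag differs. That share is not a model covariate, so no planned standardized difference would reveal it. The information is in the claims; the flag discards it.

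The subgroup problem needs no difference between the groups. If C44-only patients count as cancer patients, an effect confined to other cancers is averaged with a null.

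**Working it through.** The protocol gives no cancer prevalence, C44 share, cancer-specific rate or sample size, so there is no stated figure to reproduce. Every input below is an assumption.

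**1. Hidden imbalance after matching on the pooled flag.** Let T be the prevalence of other cancer and L that of C44 only, with subscript r for recipients and c for comparators before matching. If matching equalises the flag and nothing else separates the two types, matched comparators have

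T\* = (T_r + L_r) × T_c / (T_c + L_c).

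With a true vaccine rate ratio of 1, risk ratio R for other cancer and 1 for C44, the apparent rate ratio is [1 + T_r(R − 1)] / [1 + T\*(R − 1)].

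Assume, for ages 65 or over, T_r = T_c = 6%:

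| L_r / L_c | T\* | Apparent RR, R = 4 | Standardized difference, other cancer (absolute) |
|---|---|---|---|
| 4% / 3% | 10% × 6/9 = 6.67% | 1.18/1.20 = 0.983 | 0.027 |
| 5% / 3% | 11% × 6/9 = 7.33% | 1.18/1.22 = 0.967 | 0.053 |
| 6% / 3% | 12% × 6/9 = 8.00% | 1.18/1.24 = 0.952 | 0.078 |
| 3% / 3% | 9% × 6/9 = 6.00% | 1.000 | 0 |
| 3% / 4% | 9% × 6/10 = 5.40% | 1.18/1.162 = 1.015 | not needed |

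At R = 6 the third row gives 1.30/1.40 = 0.929. The pooled flag has a standardized difference of 0 throughout. The standardized difference is (T_r − T\*) / √{[T_r(1 − T_r) + T\*(1 − T\*)]/2}.

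**2. Wider grid.** Let the balanced flag have prevalence p, with other-cancer shares f1 (recipients) and f0 (comparators). The apparent rate ratio is [1 + p·f1(R − 1)] / [1 + p·f0(R − 1)].

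- p = 0.05, 0.55/0.65, R = 2: 0.995.
- p = 0.10, 0.50/0.70, R = 4: 1.15/1.21 = 0.950, hidden standardized difference 0.084.
- p = 0.20, 0.40/0.70, R = 7 (the extreme): 1.48/1.84 = 0.804, hidden standardized difference 0.193.
- Equal shares: 1.000 for every p and R.

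**3. Partial proxies and the split.** A simulation of 1,000,000 people used PS weighting as a stand-in for ideal matching. It assumed 5% C44 only, 5% other cancer, vaccination odds ratios of 1.5 and 0.7, and R = 5. The pooled flag gave an apparent rate ratio of 0.936. Adding a chemotherapy covariate present in 40% of other cancers gave 0.952, which removes (0.064 − 0.048)/0.064, about a quarter of the bias. Splitting the flag gave 1.000.

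**4. Subgroup dilution.** If a share f of the subgroup has other cancer, with vaccine rate ratio 2 there and 1 in C44-only patients, the pooled value is [2fR + 1 − f] / [fR + 1 − f]. At f = 0.6 this is 1.60 (R = 1), 1.75 (R = 2), 5.2/2.8 = 1.86 (R = 4) and 8.8/4.6 = 1.91 (R = 7). Dilution shrinks as R rises, because C44-only patients then contribute few events.

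**The case against.** The strongest reply is that the cohort bias is hypothetical. It needs a C44 share that differs by exposure, and the protocol gives none. The reverse mix is plausible: under Sections 9.3.1.2 and 17.2.3 an outpatient evaluation visit makes someone a comparator, so a skin-care visit can itself qualify. This stands, and it is why the point is conditional.

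The PS also holds terms that partly separate treated cancer from skin lesions: systemic immunomodulators including "Chemotherapeutic Agents", blood-disorder codes for chemotherapy-related anemia and pancytopenia, immunocompromised status and utilization counts. Empiric covariates and an outcome-specific PS are allowed. The terms already in the model reduce the bias; the optional steps commit to nothing about C44.

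Under the main inputs the hidden standardized differences (0.03 to 0.08) fall below the 0.1 limit, so a separate balance row alone would have read as balanced. That stands too, and it means the remedy has to be a model term. Other comorbidity flags are equally mixed (the kidney list holds both stones and end-stage disease), and C44 is a malignancy, so the list matches its label. This is an improvable choice, not a contradiction.

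Three stronger readings are tempting and unsupported:

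- **The vaccine would look safer.** The direction depends on an unknown mix; the reversed case gives 1.015.
- **Flagged recipients have mainly C44.** Even the assumed inputs put C44 only at 4/10 to 6/12, or 40-50%, of flagged recipients.
- **Omitting the flag would avoid the bias.** That follows only if other cancers are equally common before matching. With other cancers at 8% against 6%, C44 only at 5% against 3%, and R = 4, the unmatched factor is 1.24/1.18 = 1.051. Matching on the pooled flag gives 1.24/1.26 = 0.984, so it helps.

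**Conclusion.** The pooling is in the text, and so is a balance check that cannot see inside the flag. The consequence for the Phase 2 rate ratios is conditional and small. It is about 2-7% if C44 is over-represented among recipients as assumed for ages 65 or over, nil with an equal mix, and opposite in sign with a reversed one. These figures ignore the other PS terms, which recover part. They also apply to older adults, whereas the cohort enrols from 6 months. Larger values need extreme inputs. All are small beside the rate ratio above 3.0 that, with P below 0.01, defines a safety signal in Section 9.3.2, though such a bias could blur a modest increase. Phase 1 is unaffected, because the within-person comparison does not use the PS and cancels time-fixed traits.

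The subgroup dilution does not depend on a differential mix: a true 2 reads about 1.6-1.9 when 60% have other cancer. A reader might also infer a larger confounding bias inside the subgroup, since everyone there carries the flag. On the same inputs at R = 4 the factor would be 2.8/3.0 = 0.93 to 2.5/3.0 = 0.83. This rests on the same undocumented mix and ignores the rest of the PS, so I do not rely on it.

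That other cancers carry more risk than C44 for these outcomes is an assumption here; the protocol does not state it.

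**What to change.** Replace the single term with two binary terms, C44 only and any other listed C code, in Section 9.3.3, the PS equation and the balance table. Define the cancer subgroup in Section 9.7.2.4 by the second term, or report it with and without C44-only patients.

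The protocol version is dated 18 March 2026 and the final report is planned for 30 April 2026, so matching may already be done. In that case, report standardized differences for both components and add a sensitivity analysis that adjusts the outcome models for both, whether or not either exceeds 0.1.

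The cost is one extra PS term, one code-list line and a somewhat smaller cancer subgroup.
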